11.1 Adverse events

11.1.1 Definition of adverse events and reactions

Adverse events (Adverse Event, AE) refer to any adverse symptoms, abnormal signs, and abnormal laboratory results after the intervention study, whether there is a causal relationship with the intervention. Any adverse events, including those provided by the subjects voluntarily or obtained through inquiry by the researcher or by physical examination, laboratory examination, or other examination methods, should be recorded on the CRF and actively handled, followed closely until remission or condition is stable.

Adverse reactions (Adverse Drug Reaction, ADR): harmful, rather than desirable, results in a causal relationship with drug use during the normal application of the drug at the prescribed dose.

11.1.2 Records of adverse events

(1) All adverse events must be tracked, and the researcher must record them in the corresponding section of the case report form and record the adverse events in detail.

(2) Adverse event content: name of symptom or sign or diagnostic name of disease or laboratory examination of an indicator abnormality.

(3) Date of onset of adverse events: date of the first occurrence of AE or related symptoms AE subjects.

(4) End date of adverse events: date of cessation of AE or AE-related symptoms. If the AE still exists, do not fill in the end date.

(5) Evaluation of the severity of adverse events

Mild: symptoms and signs present, but can tolerate, generally without treatment

Moderate: Symptoms or signs cause discomfort, daily activities are limited, appropriate treatment can be taken

Severe: no ability to work and daily activities, need active treatment

(6) Measures taken :discontinuation of the relevant medication or treatment ; use of therapeutic measures; and no measures are taken.

(7) Result of adverse events: persistence, improvement, mitigation

(8) Evaluation of the correlation between adverse events and anesthesia:

Five-level evaluation criteria:

Positive correlation: adverse events appear under a reasonable time order after anesthesia;

The anesthetic method used to explain adverse events is more reasonable than other causes;

The pattern of adverse events is consistent with the pattern of adverse reactions caused by such anesthesia.

Maybe relevant: adverse events appear under the reasonable time order after anesthesia;

The use of anesthesia to explain adverse events is more reasonable than other causes; but do not rule out other reasons.

It may not be relevant: the occurrence of adverse events does not conform to the reasonable time order after anesthesia; (Other causes may cause adverse events, but the possibility of anesthesia can not be ruled out;None: The possibility of adverse events resulting from or excluding from anesthesia by other causes);

Can not be determined: the occurrence of adverse events does not conform to the reasonable time order after anesthesia; However, it is impossible to determine whether it is related to anesthesia, nor can it be explained by other reasons.

11.2 Serious adverse events

11.2.1 Definition of serious adverse events (SAE)

In the course of clinical trials, such events as hospitalization, prolonged hospitalization, disability, affecting working ability, endangering life or death, causing congenital malformation, etc.

11.2.2 Serious adverse event handling process

When serious adverse events occur, we should make every effort to rescue and actively take various measures to avoid permanent damage. The SAE researcher must notify the applicant, clinical trial organization, ethics committee by telephone or fax within 24 hours from the beginning of the trial to the observation period, and fill in the section of the case report form on serious adverse events. SAE's medical information should also be reported to the applicant after 24 hours.

11.2.4 Responsibilities of severe adverse events researcher

When a severe adverse event occurs, the researcher should actively take appropriate medical measures, carry out rescue treatment, and notify the above responsible person by telephone or fax within 24 hours.

11.2.6 Responsibility of applicants for serious adverse events

Assist researchers to report serious adverse events and take necessary measures to ensure the safety of subjects.

11.2.7 Responsibility of the Inspector for Serious Adverse Events

Assist researchers to report serious adverse events and take necessary measures to ensure the safety of subjects.

11.3 Adverse reactions recorded in (CRF) of the case report form

All adverse reactions should be recorded in the case report form (CRF) adverse events.

12. Data management and statistical analysis

12.1 Input of case report form and completion of original record form

This study adopts an electronic case report form; researchers should input in time to ensure accurate content and timely summary. The paper original record form is used to record the study's relevant data, generally should not be altered, if there is an error that needs to be modified, it should sign at the modification place and sign the date of modification. The completed original record form should be entered immediately into the electronic medical record report form.

12.2 Data entry and modification

12.2.1 Source file definitions

The source file is the first-hand information of clinical trial data recording. This clinical study's source documents refer to the research medical records, informed consent, physical and chemical examination reports, drug management documents, quality inspection documents, etc.

12.2.2 Data recording and reporting

Any observation and inspection results in the study should be recorded in the source file in a timely, accurate, complete, standardized, and true manner.

Changes to source files and source data must be sufficiently substantiated. Otherwise, the first judgment (a record) shall prevail.

Data reporting uses a network-based "electronic CRF and data management system."

Data entry: independent double timely input.

The advantages of electronic CRF and data management system: to ensure that the organizer can grasp the dynamic of each center test in time; to facilitate the quality controller to review and question the data of each center in time through the network platform, to improve the working efficiency and reduce the cost of quality control; to set the data rules and ensure the quality of the data through the network CRF;; to input the CRF data from each center to help each center find

problems in time and correct them, and to export the data entered by the center for academic papers with the permission of the team leader; After the completion of the test, faster and more accurate completion of the statistical analysis report.

12.2.3 Data verification requirements

The Data Monitoring Committee will conduct a mid-term evaluation of the research data, monitor the data, and hold occasional meetings to evaluate the research data's security and effectiveness.

During site inspection (SDV), clinical research institutions shall provide convenience and consult in prescribed places.

Data audit method: the inspector logs in the data monitoring end of the electronic CRF and data management system in each center and uses the online method to confirm the inconsistent data input. 100% check the consistency of electronic CRF data with source data such as research medical records.

The reference of source documents should follow hospital medical documents' regulations and the regulations of archives of drug clinical research institutions.

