- 1) Is there any difference between general anesthesia and local anesthesia in the occurrence, severity, attack type, and delirium duration after hip fracture in the elderly? Which anesthetic method can reduce the incidence of postoperative delirium?
- 2) Is there a difference in the effect of the two anesthetic methods on postoperative delirium in different older people (elderly, dementia, or delirium)?
- 3) Do various factors (hypotension, drugs, pain, etc.) during anesthesia affect postoperative delirium and extent?
- 4) To analyze whether the control of anesthesia can reduce the medical expenses and related economic benefits caused by delirium.
- 5) The relationship between the classification and duration of delirium and patients' prognosis; does delirium lead to long-term cognitive dysfunction? How does it affect patients and their families' quality of life? The survival rate in patients with delirium?

2. Research topics

A randomized, controlled, multicenter, prospective study of the effect of local and general anesthesia on postoperative delirium in elderly patients with hip fractures

3. Purpose of the study

To evaluate the effect of two anesthetic methods on the incidence and prognosis of delirium in elderly hip fracture

4. Research Design

using prospective, multicenter, large sample, randomized controlled study design. Randomly enter local anesthesia group or general anesthesia group at 1:1.

According to the domestic literature report of postoperative delirium in elderly patients, the sample size estimation estimated that postoperative delirium incidence is about 26. Assuming that postoperative delirium incidence after local anesthesia is less than 30% of general anesthesia, the calculated sample size is 441 $n\alpha=$ each group. The provisional total sample size is 1000 cases. The sample size can be adjusted according to the progress of the study and the results in the medium term.

The number of cases in each center is 100. Because of the central random system, the number of cases in each center can be automatically adjusted according to the actual situation of the subjects recruited.

5. Case selection

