12.4.4 Data management and statistical analysis software

1. Data management and statistical analysis software

Beijing Baiaozhi Information Technology Co., Ltd. clinical research integrated information platform (www.bioknow.net), using double independent input, check the correct statistical analysis. The statistical analysis adopts SAS9.13 software programming analysis.

(2) Setting of parameters in statistical analysis

The bilateral test (two-side test) was used for all hypothesis tests, and the α was 0.05. $P \leq 0.05$, the reliability of all confidence intervals was 95.

13. Test management

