3.3 Power and Sample Size

Based on the previously published incidence of postoperative delirium diagnosed using Confusion Assessment Method ranged from 28% to 50% in the elderly patients (age 65) during the hospital stay for hip fracture surgery, the observational studies in China estimated 3-day postoperative delirium incidences of 11.1%–23.3%.⁴⁻⁶ Assuming postoperative delirium incidences in general anaesthesia OF 26% and a reduction of 30% postoperative delirium in RA, 441 patients should be needed for each group to give power (1- β) of 80% and the significance level of 5% (two-sided). With an estimated drop-out rate of 10%, a total of 1000 patients will be recruited from the nine clinical trial centers in China.

4. Statistical Principles

Statistical analysis will be conducted in accordance with the plan outlined in the SAP. Statistical analysis will abide by these general statistical principles below.

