4.3 Multiple Comparisons

The primary outcome will be tested at 5% (two-sided) significance level. No corrections will be made for multiple comparisons, so intervals should not be used to infer treatment effects. As described in our research proposal, each comparison made will be hypothesis-driven and not hypothesis-generating.

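### The committee is to evaluate effectiveness mid-trial and the sample size may change on mid-term results, but no rule says what a look may lead to, so the 5% error rate is not assured

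*Protocol*

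**What the plan says.** Protocol 12.2.3 states: "The Data Monitoring Committee will conduct a mid-term evaluation of the research data". The same sentence has the committee "hold occasional meetings to evaluate the research data's security and effectiveness". One mid-term evaluation is named, without a date or information fraction. The number of further meetings is left open.

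Protocol section 4 adds an action that may follow from interim data: "The sample size can be adjusted according to the progress of the study and the results in the medium term". It does not say whether those results are pooled or by arm, or how they would change the number.

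The significance level is set as for a single analysis. Protocol 12.4.4 says "The bilateral test (two-side test) was used for all hypothesis tests, and the α was 0.05". SAP 4.3 says "The primary outcome will be tested at 5% (two-sided) significance level". SAP 3.3 sizes the trial for one such test at 80% power.

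The supplied text contains no interim-analysis section, stopping boundary, alpha-spending rule or re-estimation rule, and no statement that interim data will not be used to stop for efficacy. The termination criteria in Protocol 5.4 do not mention efficacy. The SAP names the data monitoring body only in its abbreviation list.

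**The concern.** A two-sided 5% test has a 5% error rate if the data are tested once, or if earlier looks cannot lead to a claim, an early end or a results-driven change in design. Here the committee is asked to judge effectiveness and the sample size is open to mid-term results, yet nothing limits what a look may lead to.

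The main conclusion about regional versus general anaesthesia rests on this one test. If an interim comparison were acted on at the ordinary 5% level, the false-positive risk would exceed the stated level. A trial stopped early on such a comparison would also tend to overstate the effect.

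**Working it through.** **Step 1. Reproduce the design as planned.** SAP 3.3 gives the inputs: "Assuming postoperative delirium incidences in general anaesthesia OF 26% and a reduction of 30% postoperative delirium in RA", 80% power and two-sided 5%. The regional rate is 0.26 × 0.70 = 0.182, a difference of 0.078. With the unpooled normal formula:

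n = (1.960 + 0.842)² × (0.26 × 0.74 + 0.182 × 0.818) / 0.078² = 7.849 × 0.341276 / 0.006084 = 440.3, so 441 per group.

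This matches the plan; the pooled-variance formula gives 444. Allowing for 10% drop-out, 882 / 0.90 = 980, which the plan rounds up to 1000. The design therefore contains one 5% test and no allowance for interim looks.

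**Step 2. Error rate if the named look could be acted on.** *Assumption, because the documents give no rule:* the mid-term look could end the trial or support a claim at two-sided p<0.05, and the final test is also at 0.05. At information fraction t, the interim and final z-statistics under the null are bivariate normal with correlation √t. Overall type I error is

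1 − P(|Z₁| < 1.96 and |Z₂| < 1.96).

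| Timing of the look (t) | Correlation √t | Overall type I error |
|---|---|---|
| 0.30 | 0.548 | 8.9% |
| 0.50 | 0.707 | 8.3% |
| 0.70 | 0.837 | 7.6% |

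If the look is never acted on, only the final test counts and the error is 5%.

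**Step 3. Further looks, as a hypothetical.** If occasional meetings also compared delirium by arm, at equal spacing and each able to stop at p<0.05, the error would be 10.7% with two interim looks, 12.6% with three and 14.2% with four (final test added in each case). The documents do not establish any of these schedules.

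**Step 4. Effect on the estimate.** Take the planned rates (true relative risk 0.70) and assume one look at 250 per arm, half of the 500 recruited per arm. By simulation, a stop in favour of regional anaesthesia at p<0.05 would occur in about 56% of trials, with a geometric mean relative risk of about 0.62 among those stopped. With a threshold of p<0.001 the chance of such a stop falls to about 12%.

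**Step 5. Error rate under the proposed boundary.** Replace 1.96 at the interim by 3.29 (two-sided p<0.001, either direction) and keep 1.96 at the end. For one look at half the information the overall error is 5.02%. It is 5.05% for a look at 30% and 5.00% at 70%. The final test is unchanged, so the planned 441 per group stands.

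**The case against.** The strongest reply is that looking at data does not inflate the error rate; acting on it does. No sentence lets the committee stop for efficacy or declare a result early. The SAP cites a 2017 publication, so it is later than the July 2014 protocol. It says that analysis will follow its own plan, and that plan holds one primary test. This stands in part. It rules out saying that the plan's error rate *is* 8.3%. But the SAP is silent on interim looks and does not forbid them, and Protocol section 4 does allow one action on mid-term results, a change in sample size.

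A second reply is that the committee sentence sits among data-verification rules in a translated text, so it could concern the security and validity of the data. That reading is possible. Protocol 12.4.1, however, calls the safety population the security data set and uses effectiveness for the primary efficacy evaluation, so safety and efficacy is the better reading. If data quality was meant, one sentence saying so would settle that part.

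Third, a committee charter might hold the rules. None was supplied and part of the SAP was removed before review, so absence is judged on the text available.

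A reader might also infer that the open number of meetings puts the error at 10% to 14%. The documents do not support that: only one mid-term evaluation is named, and nothing says that the other meetings compare delirium by arm. Nor do the subjective outcome and the visible anaesthetic technique strengthen the point, since neither affects error inflation from repeated looks.

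**Conclusion.** The point holds in conditional form. An effectiveness review and a results-based change in sample size are both provided for, the full 5% is kept for the primary test, and no rule connects them. The stated error rate is therefore unprotected, which is more than a missing detail.

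The headline size is about 8.3% for the one named look (7.6% to 8.9% by timing), assuming that look could end the trial or support a claim at p<0.05. It would be higher if further meetings compared delirium by arm, and 5% if no look is acted on. A sample-size change driven by unblinded results could also move the error rate; it is not sized here because no rule is given.

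A reader might infer that the trial will stop early for efficacy, or that its 5% level is already broken. Neither follows from the documents. The change is worth making because it is cheap and protects the only primary claim.

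**What to change.** In Protocol 12.2.3 and in a new SAP paragraph, state one of two options:

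- **(a)** No between-arm comparison of the primary outcome is used for stopping or for changing the sample size before database lock.
- **(b)** The primary outcome is compared by arm only at the planned mid-term look, under a symmetric Haybittle-Peto boundary: no stop for a difference in delirium in either direction unless two-sided p<0.001. The final test stays at 0.05. Any change in sample size uses only pooled, blinded data.

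The boundary should be symmetric because both arms are active and delirium is itself a harm, so a benefit in one arm is a harm in the other. Under either option, occasional meetings carry no formal comparison of the primary outcome, and the committee's safety review of other events is unaffected. Protocol section 4 should refer to whichever rule is chosen.

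The cost is one paragraph in each document and no extra patients. The downside is giving up an early stop on a weak interim signal.

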12.2.4 Requirements for Data Questions and Answers

Issue of questions: questions issued in logical checks and questions issued during SDV are regularly logged into the system by the CRC- data entry officer, and the organization's questions are downloaded to generate a data clarification table (DCF).

Question answering: the CRC- data entry staff will DCF the corresponding researcher to answer questions; the data is modified on the DCF, DCF saved as the source file.

Online update: CRC- data entry will answer questions on the DCF online data update.

Solution: the inspector SDV, the DCF, checks its authenticity and rationality; the project data manager verifies the answer data," confirms the correct, "or" issues a new question "when there is still a problem or a new problem. The question is deemed to be resolved.

Data entry is the responsibility of the designated data administrator. In order to ensure the accuracy of the data, two data administrators should independently input and proofread.

The data manager will question the case report form (DRQ) questions and send questions to the researcher through the clinical inspector. The researcher should answer and return them as soon as possible. The data manager will modify, confirm, and input the data according to the researcher's answer and issue the DRQ. again if necessary

12.3 Data locking

After confirming that the established database is correct, the data is locked by the principal researcher, the applicant, and the statistical analyst. Locked data files are no longer changed in principle.

Statistical analysis

12.4.1 Analysis of data sets

(1) Total Analysis Set (FAS): A collection of all cases randomly enrolled and treated with at least one trial drug.

When analyzing the main curative effect index, the FAS concentration's missing value is processed by carrying the results observed at the last time point to the current (LOCF) method.

An Available Case Analysis principle is used to deal with the missing value in the analysis of secondary efficacy index, general condition, and safety.

(2) Conformity with program set (PPS): a collection of cases that meet the inclusion criteria and complete treatment in accordance with the provisions of the trial program, i.e., cases that meet the trial program, have good compliance, have not taken banned drugs, and have completed the evaluation of effectiveness (at least primary efficacy), if any.

(3) Security data set (SAS): at least one treatment and actual data recorded with a safety indicator evaluation.

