4.5 Missing Data

In the primary outcome analysis, postoperative delirium, the missing values in Full Analysis Set will not be imputed.

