4.6 Analysis Populations

All analyses of primary and secondary outcomes, including safety outcomes, will be based on intention-to-treat. Participants would be analysed in the intervention group to which were randomised, and all participants shall be included whether or not they received the allocated intervention.

As a sensitivity analysis, a per-protocol analysis would also be carried out for the primary outcome and secondary outcomes.

5. Definition and Derived variables

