5.2 Secondary outcomes

Severity and Subtypes

The 13 items from Delirium Rating Scale-Revised-98 contribute to a severity score (items are scored zero to three, range from zero [no delirium] to 39 [maximum severity]) including two items which also define hyperactive (score ≥ 1 on motor agitation), hypoactive (score ≥ 1 on motor retardation), mixed motor (score ≥ 1 on both motor items) or no motor (score=0 on both motor items) subtypes of delirium.

Visual analogue scale (VAS)

Pain scores are measured using VAS (ranges from 0 [no pain] to 100 [worst pain], assessed daily, over the seven days and the highest pain score will be reported as continuous data. The first three days' VAS also will be analysed by comparison between groups.

30-day mortality is all-cause mortality during 30 days post-surgery.

Length of hospital stay is calculated from the first post-operative day to discharge.

Costs of the anaesthetic procedure include the expenditure of anaesthesia; anaesthetic drug, and labour cost.

Total in-hospital costs include the expenditure of anaesthesia, surgery, and hospitalisation.

5.3 Subgroups:

Pre-delirium is defined as whether patients had delirium before the intervention, using the Confusion Assessment Method on the day of admission.

Pre-existing dementia is defined by the Mini-Mental State Examination (MMSE) score with thresholds adjusted for educational levels.

- MMSE scores from 0 to 17 without educational experience/illiteracy;
- MMSE scores from 18 to 20 with an educational level less than primary education;
- MMSE scores from 21 to 22 with an educational level less than high school diploma;
- MMSE scores from 23 to 24 with an educational level less than a bachelor's degree.

Age is categorised by groups 65 to 80 years vs >80 years.

6. Trial Population

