6.2 Baseline Characteristics

Categorical data will be summarised by frequencies and percentages. Continuous data will be summarised by the number of responses, mean and standard deviation if deemed to be normally distributed, and the number of responses, median and interquartile range or total range if data appear skewed. Tests of statistical significance will not be undertaken, nor confidence intervals presented ⁷.

7. Statistical Analysis

7.1 Primary outcome:

The primary outcome is the incidence of postoperative delirium during 7 postoperative days, diagnosed with the Confusion Assessment Method, and will be a categorical variable.

7.2 Secondary outcome measures are as follows:

- The subtype, severity, and duration of delirium in 7 days after the surgery, diagnosed with the Delirium Rating Scale-Revised-98 and confusion Assessment Method, subtypes and duration of delirium are categorical variables, and severity score is a continuous variable;
- Duration of delirium, measured by days from the onset of delirium symptom to the resolution of symptoms, which is a continuous variable;
- The intensity of postoperative pain, measured with acute pain score in 7 days after the surgery using Visual Analogue Scale (VAS), which is a continuous variable;
- The occurrence of non-delirium in-hospital complications within 30 days after surgery, including chest infection, myocardial infarction, renal failure, gastrointestinal ileus, which is a categorical variable;
- Length of hospital stay, measured by the sum of inpatient days from admission to discharge, which is a continuous variable;
- Mortality during the hospital stay and during the follow-up period after hospital admission, which is a categorical variable;
- Incidence of delirium in the clinic or at the residence on 30-day, 6 months, 12 months after surgery, diagnosed with CAM, which is a categorical variable;
- Cognitive and functional decline on 30-day, 6 months, 12 months after surgery, diagnosed with Mini-Mental State Examination (MMSE) and Hospital Anxiety and Depression Scale, which is a categorical variable;
- Quality of life on 30 days, 6 months, 12 months after surgery, using 36-Item Short Form questionnaire, which is a categorical variable;

- Economic parameters, including total cost in hospital and expenditure for anesthesia and resource using costs, including equipment and disposables required for each anesthetic technique, which are the continuous variables.

8. Analysis Methods

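### Late delirium, cognition and quality of life are compared among survivors only, and no rule says how an in-hospital death enters length of stay

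*Protocol*

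**What the plan says.** **Rule for missing values.** Protocol 12.4.1 carries the last observation forward for the primary outcome. For everything else it says: "An Available Case Analysis principle is used to deal with the missing value in the analysis of secondary efficacy index, general condition, and safety". SAP 4.5 addresses the primary outcome alone: "In the primary outcome analysis, postoperative delirium, the missing values in Full Analysis Set will not be imputed". It says nothing about secondary outcomes.

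**Population.** SAP 4.6 states: "All analyses of primary and secondary outcomes, including safety outcomes, will be based on intention-to-treat". It adds that every participant is included, whatever treatment was received.

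**Late outcomes.** SAP 7.2 lists three:
- "Incidence of delirium in the clinic or at the residence on 30-day, 6 months, 12 months after surgery, diagnosed with CAM"
- "Cognitive and functional decline on 30-day, 6 months, 12 months after surgery", assessed with the MMSE and the HADS
- "Quality of life on 30 days, 6 months, 12 months after surgery, using 36-Item Short Form questionnaire"

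All three are typed as categorical. Cognition, function and quality of life also form Aim 7 in SAP 2.2; mortality is Aim 6 and a separate outcome. SAP 8.2 gives methods for SO1 to SO5 only, so it has none for the late outcomes or for mortality.

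**Length of stay.** SAP 5.2 says: "Length of hospital stay is calculated from the first post-operative day to discharge". SAP 7.2 starts the count at admission instead. SAP 8.2 (SO5) plans a median with interquartile range and a generalised linear model. None of the three places mentions death.

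**The concern.** A patient who dies before the 6- or 12-month visit has no CAM, MMSE, HADS or SF-36 result. Under an available-case rule that patient leaves the comparison. What remains is a group selected by an event after randomisation, and the two arms' survivors need not be alike.

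The protocol's own background section gives reason to expect death and decline to travel together. It says that delirium raises mortality, links it to dementia, and reports poor mortality and function in patients with persistent delirium. The population is 65 or older, ASA I to IV, with hip fracture, so some deaths within a year are to be expected. An arm that lost more of its vulnerable patients could then show less cognitive decline and better quality of life among those left, and a reader of the Aim 7 results could take that for a benefit.

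Length of stay raises a related question, because death in hospital also ends the stay.

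**Working it through.** The plan gives no figure for mortality, late decline or stay, so there is nothing to reproduce on this point. Every input below is an assumption, chosen to show direction and range.

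**1. Survivors-only comparison, 20% versus 25% dead at 12 months.** Arm A: 20% dead, and 30% of the 80% alive have declined, so 0.30 × 80 = 24% of those randomised. Dead or declined: 20 + 24 = 44%. Arm B is the same except for 5 points more deaths.

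| Share of extra deaths who would have declined | Alive with decline, B | Decline among B's survivors | Survivor RR, B vs A | Dead or declined, A vs B |
|---|---|---|---|---|
| 100% | 24 − 5.0 = 19.0% | 19.0/75 = 25.3% | 25.3/30.0 = 0.84 | 44.0% vs 44.0% |
| 70% | 24 − 3.5 = 20.5% | 20.5/75 = 27.3% | 27.3/30.0 = 0.91 | 44.0% vs 45.5% |
| 30% (death unrelated to decline) | 24 − 1.5 = 22.5% | 22.5/75 = 30.0% | 1.00 | 44.0% vs 47.5% |

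At other mortality levels, with all extra deaths among would-be decliners:
- 10% vs 15%: (27 − 5)/85 = 25.9%, RR 0.863
- 15% vs 20%: (25.5 − 5)/80 = 25.6%, RR 0.854

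**2. A second parameterisation.** Let q be the share who would be impaired if all lived (30% in both arms), m mortality, and s the share of deaths who would have been impaired. Impairment among survivors is (q − s·m)/(1 − m). One arm has m = 10%.

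| Mortality in the other arm | RR, s = 0.3 | RR, s = 0.6 | RR, s = 0.9 |
|---|---|---|---|
| 12% | 1.00 | 0.972 | 0.935 |
| 15% | 1.00 | 0.926 | 0.832 |
| 20% | 1.00 | 0.844 | 0.643 |

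Dead or impaired is q + m(1 − s). For 10% vs 15% mortality it is 34.0% vs 36.0% at s = 0.6 and 31.0% vs 31.5% at s = 0.9, so it no longer favours the arm with more deaths.

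Equal mortality does not remove the problem if death selects differently by arm. With m = 10% in both, s = 0.6 gives 0.24/0.90 = 26.7% and s = 0.9 gives 0.21/0.90 = 23.3%, RR 0.875.

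**3. Length of stay, if days are counted to death.** Assume a mean of 14 days in survivors and death at day 5. The mean stay is 14(1 − m) + 5m = 14 − 9m. In-hospital mortality of 2% gives 13.82 days; 3%, 4% and 7% give 13.73, 13.64 and 13.37. The arm with more deaths looks 0.09, 0.18 or 0.45 days shorter. If the patient is dropped instead, the comparison is again among survivors.

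**The case against.** **The available-case rule may not govern.** It stands in a 2014 protocol version and speaks of missing values, while the SAP calls for intention-to-treat with everyone included. That is fair, but it does not help. Intention-to-treat fixes the arm in which a patient is counted; it supplies no MMSE or SF-36 for someone who has died. Until death is given a value, survivors are all that can be analysed, whichever document prevails.

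**The illustration is built to show the effect.** This stands. The RR of 0.84 needs 5 points more deaths, all in would-be decliners. It also turns no difference (44% in both arms) into an apparent benefit, which is not a reversal; only the 70% case reverses direction, against a 1.5-point difference in the composite. With 500 per arm and complete follow-up, 30.0% vs 25.3% in 400 and 375 survivors gives z of about 1.45, while 20% vs 25% mortality gives about 1.9. Mortality is reported separately, so the deaths would probably be more visible than the artefact. A separate mortality line still does not correct the late-outcome estimate.

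**The composite can mislead too.** This also stands: 44% vs 44% hides 5 points of extra mortality. It should therefore not be the sole Aim 7 result.

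**A stronger reading on length of stay.** A reader might infer that the plan counts an in-hospital death as a short stay. No section says so. Death could be coded as discharge, censored, or left without a discharge date. Moreover, a few percent of early deaths would hardly move a median; the generalised linear model is more exposed.

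**Conclusion.** The point holds as a gap in the plan. No value is given to death, so the 6- and 12-month delirium, cognition and quality-of-life comparisons are conditional on survival. The size cannot be known from the documents. Under the assumed 20% vs 25% mortality, the survivor RR is 0.84 to 0.91 in favour of the arm with more deaths when 100% to 70% of the extra deaths are would-be decliners. There is no bias when death is unrelated to decline. Across the wider assumed grid the RR runs from 0.64 to 1.00. The bias needs two things: deaths concentrated in patients who would have declined, and mortality (or selection by death) that differs between arms.

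The documents do not support saying that either anaesthetic raises mortality, that these comparisons will be biased, or that their direction will reverse. For length of stay the finding is silence on death, with a probably small effect on the median. These are secondary outcomes, and the primary outcome is unaffected. The change is worth making but does not threaten the trial's main conclusion.

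**What to change.** In SAP 7.2 and 8.2:

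1. For each categorical 6- and 12-month outcome, report the relative risk of being dead or impaired in all randomised patients of known status. Put its two components beside it: mortality, and impairment among survivors.
2. Label the survivors-only comparison as conditional on survival and not a randomised comparison.
3. Define impairment for each outcome. SAP 7.2 gives no cut-off for decline on the MMSE or HADS and no categories for the SF-36, so the composite cannot be computed as the text stands. Add the analysis methods for late outcomes and mortality that SAP 8.2 lacks.
4. For SO5, state that in-hospital death is not a discharge. Analyse time to discharge alive with death as a competing event, or rank deaths as the longest stay. Reconcile the two starting points for the stay in SAP 5.2 and 7.2.

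The cost is SAP wording and a modest amount of analysis. Mortality in hospital, at 30 days and at 6 and 12 months is already listed in Protocol Table 2. The drawback is that the composite mixes death with decline and can mask components that move in opposite directions, so the components must always be shown with it.
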